- Female subjects of childbearing potential should be willing to use 2 methods of birth control or be surgically sterile, or abstain from heterosexual activity for the course of the study through 120 days after the last dose of study medication (Reference Section 5.7.2). Subjects of childbearing potential are those who have not been surgically sterilized or have not been free from menses for > 1 year.
- 12. Male subjects should agree to use an adequate method of contraception starting with the first dose of study therapy through 120 days after the last dose of study therapy.
- 13. Patient is < 5 years free of another primary malignancy, except: a) if the other malignancy is basal cell carcinoma or cervical carcinoma in situ or b) if the other primary malignancy is not considered clinically significant and is requiring no active intervention

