- 7. Has an active automimmune disease requiring systemic treatment within the past 3 months or a documented history of clinically severe autoimmune disease, or a syndrome that requires systemic steroids or immunosuppressive agents. Subjects with vitiligo or resolved childhood asthma/atopy would be an exception to this rule. Subjects that require intermittent use of bronchodilators or local steroid injections would not be excluded from the study. Subjects with hypothyroidism stable on hormone replacement or Sjogren's syndrome will not be excluded from the study.
- 8. Has evidence of interstitial lung disease or active, non-infectious pneumonitis.
- 9. Has an active infection requiring systemic therapy.
- 10. Has a history or current evidence of any condition, therapy, or laboratory abnormality that might confound the results of the trial, interfere with the subject's participation

for the full duration of the trial, or is not in the best interest of the subject to participate, in the opinion of the treating investigator.

- 11. Has known psychiatric or substance abuse disorders that would interfere with cooperation with the requirements of the trial.
- 12. Is pregnant or breastfeeding, or expecting to conceive or father children within the projected duration of the trial, starting with the pre-screening or screening visit through 120 days after the last dose of trial treatment.
- 13. Has received prior therapy with an anti-PD-1, anti-PD-L1, anti-PD-L2, anti-CD137, or anti-Cytotoxic T-lymphocyte-associated antigen-4 (CTLA-4) antibody (including ipilimumab or any other antibody or drug specifically targeting T-cell co-stimulation or checkpoint pathways). Patients who have previously received MK-3475 or participated in an MK-3475 clinical trial will be ineligible.
- 14. Has received prior therapy with vorinostat or other epigenetic agent.
- 15. Has a known history of Human Immunodeficiency Virus (HIV) (HIV 1/2 antibodies).
- 16. Has known active Hepatitis B (e.g., HBsAg reactive) or Hepatitis C (e.g., HCV RNA [qualitative] is detected).
- 17. Has received a live vaccine within 30 days prior to the first dose of trial treatment.
- 18. Requires total parenteral nutrition and is unable to swallow pills or unable to take a suspension through a gastrostomy tube.

5.1.4 Inclusion and Exclusion Criteria for Second Course Phase (Retreatment Period for Post-Complete Response Relapse ONLY)

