Subjects may be eligible to receive MK-3475 in the Second Course Phase of this study if the study remains open and the subject meets the following conditions:

- Stopped initial treatment with MK-3475 after attaining an investigator-determined confirmed response according to RECIST1.1 response criteria
- Was treated for at least 24 weeks with MK-3475 before discontinuing therapy
- Received at least four treatments with MK-3475 beyond the date when the initial CR was declared
- Experienced an investigator-determined confirmed cutaneous or radiographic disease progression after stopping their initial treatment with MK-3475
- Did not receive any anti-cancer treatment since the last dose of MK-3475

- Have a performance status of 0 or 1 on the ECOG Performance Scale
- Demonstrate adequate organ function as detailed in Section 5.1.2
- Female subject of childbearing potential should have a negative urine or serum pregnancy test within 72 hours prior to receiving retreatment with study medication.
- Female subjects of childbearing potential should be willing to use 2 methods of birth control or be surgically sterile, or abstain from heterosexual activity for the course of the study through 120 days after the last dose of study medication (Reference Section 5.7.2). Subjects of child bearing potential are those who have not been surgically sterilized or have not been free from menses for > 2 year.
- Male subjects should agree to use an adequate method of contraception starting with the first dose of study therapy through 120 days after the last dose of study therapy.
- Does not have a history or current evidence of any condition, therapy, or laboratory abnormality that might interfere with the subject's participation for the full duration of the trial or is not in the best interest of the subject to participate, in the opinion of the treating investigator.

Subjects who restart treatment will be retreated using the same guidelines for the combination of MK-3475 and vorinostat.

Visit and response criteria requirements are outlined in Section 6.1 – Trial Flow Chart for the second course

Patients upon progression might have requested an experimental biopsy to investigate tumor immunology at the time of progression.

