5.7.2 Contraception

MK-3475 and vorinostat may have adverse effects on a fetus in utero. Furthermore, it is not known if MK-3475 has transient adverse effects on the composition of sperm. Non-pregnant, non-breast-feeding women may be enrolled if they are willing to use 2 methods of birth control or are considered highly unlikely to conceive. Highly unlikely to conceive is defined as 1) surgically sterilized, or 2) postmenopausal (a woman who is \geq 45 years of age and has not had menses for greater than 1 year will be considered postmenopausal), or 3) not heterosexually active for the duration of the study. The two birth control methods can be either two barrier methods or a barrier method plus a hormonal method to prevent pregnancy. Subjects should start using birth control from study Visit 1 throughout the study period up to 120 days after the last dose of study therapy.

Female patients of childbearing potential must have a negative serum pregnancy test (β -hCG) within 72 hours prior to receiving the first dose of vorinostat and should either be postmenopausal, free from menses for > 2 years, surgically sterilized, or willing to use 2 reliable forms of contraception simultaneously, unless abstinence is the chosen method of contraception, starting with visit 1.

Vorinostat may have adverse effects on a fetus in utero. Furthermore, it is not known if vorinostat has transient adverse effects on the composition of sperm. Adequate contraception must be used by all patients (both male and female) and their partners during therapy with vorinostat, and for 30 days after the completion of study drug administration. Women of childbearing potential should be advised to avoid becoming pregnant while receiving treatment with vorinostat.

The following are considered adequate barrier methods of contraception: diaphragm, condom (by the partner), copper intrauterine device, sponge, or spermicide. Appropriate hormonal contraceptives will include any registered and marketed contraceptive agent that contains an estrogen and/or a progestational agent (including oral, subcutaneous, intrauterine, or intramuscular agents).

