Subjects should be informed that taking the study medication may involve unknown risks to the fetus (unborn baby) if pregnancy were to occur during the study. In order to participate in the study they must adhere to the contraception requirement (described above) for the duration of the study and during the follow-up period defined in section 7.2.2-Reporting of Pregnancy and Lactation to the Sponsor and to Merck. If there is any question that a subject

will not reliably comply with the requirements for contraception, that subject should not be entered into the study.

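### Section 5.1.2 sets a laxer limit for childbearing potential and a laxer pregnancy test than Section 5.7.2, and nothing tells sites to apply the stricter text

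*Combined protocol and SAP*

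**What the plan says.** **Definition and duty.** Section 5.1.2 asks women of childbearing potential to use two methods, be sterile or abstain, "for the course of the study through 120 days after the last dose of study medication (Reference Section 5.7.2"). It then gives its own definition: "Subjects of childbearing potential are those who have not been surgically sterilized or have not been free from menses for > 1 year". No age limit is attached. For the second course, Section 5.1.4 repeats the sentence with another limit: "Subjects of child bearing potential are those who have not been surgically sterilized or have not been free from menses for > 2 year".

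Section 5.7.2 has three relevant paragraphs.
- Paragraph 1 covers all women who are not pregnant or breast-feeding. They "may be enrolled if they are willing to use 2 methods of birth control or are considered highly unlikely to conceive". The unlikely-to-conceive group is the sterilized, the postmenopausal and those not heterosexually active. The postmenopausal limit is an age of at least "45 years of age and has not had menses for greater than 1 year will be considered postmenopausal". Birth control runs to 120 days after the last dose.
- Paragraph 2 concerns women of childbearing potential on vorinostat. They should be postmenopausal, "free from menses for > 2 years, surgically sterilized, or willing to use 2 reliable forms of contraception simultaneously", with abstinence as an alternative.
- Paragraph 3 requires adequate contraception of every patient, male or female, during vorinostat and for 30 days afterwards. It has no age or amenorrhea limit.

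The section closes by making this a condition of entry: "In order to participate in the study they must adhere to the contraception requirement (described above").

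**Pregnancy test at first entry.** Item 10 of Section 5.1.2 accepts urine or serum within 72 hours before the first dose. It asks for serum only when the urine result is positive or cannot be confirmed negative. Paragraph 2 of 5.7.2 makes a negative serum test mandatory within 72 hours before the first vorinostat dose.

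**The concern.** Sections 5.1.2 and 5.7.2 cover the same women at the same entry decision and give different answers. Section 7.1.1.2 makes review of the inclusion and exclusion criteria the step that establishes whether a subject qualifies. Those criteria carry the laxer rule on both contraception and testing. The cross-reference to 5.7.2 is attached to the duty and comes before 5.1.2 states its own limit, and no precedence rule is given.

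What is at stake is fetal exposure. Section 5.7.2 says both drugs may harm a fetus. Section 5.7.3 reports that vorinostat crosses the placenta in animals, with fetal plasma levels up to 50% of maternal, and that gall bladder malformations rose with dose in rabbits. Entry is open from age 18. A second, smaller cost is avoidable protocol deviations at sites that follow the criteria list to the letter.

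**Working it through.** There is no plan figure to reproduce, so the check applies each rule to one test case and then compares the two test requirements.

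**Test case.** A woman of 40 with 14 months of amenorrhea, not sterilized and heterosexually active.

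| Rule | Comparison | Result |
|---|---|---|
| 5.1.2, evident meaning (neither sterilized nor more than 1 year without menses) | 14 > 12 months | Not of childbearing potential; no duty |
| 5.1.2, literal 'or' | Not sterilized | Of childbearing potential; two methods or abstinence |
| 5.1.4, evident meaning | 14 < 24 months | Of childbearing potential; two methods or abstinence |
| 5.7.2 paragraph 1 | 40 < 45; not sterilized; heterosexually active | Not unlikely to conceive; two methods |
| 5.7.2 paragraph 2 | 40 < 45 and 14 < 24 months | Two methods or abstinence |
| 5.7.2 paragraph 3 | No limit to test | Adequate contraception on vorinostat and for 30 days after |

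The paragraph 2 result does not depend on how its list is read. The 2-year clause may be a separate exemption, may define postmenopausal, or may be an extra condition. She fails all three, because she is under 45 and under 2 years. If 5.1.2 is said to remove her from paragraph 2 by taking her out of the childbearing-potential group, paragraph 1 still reaches her, since it is not limited to that group.

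**What is left after paragraph 3.** Take one last-dose date for both drugs; Section 5.2.1.2 bars continuing either alone.
- On treatment and to day 30: 5.7.2 paragraphs 1 and 2 ask for two methods. Someone relying on 5.1.2 would be caught only by paragraph 3, which does not say two methods.
- Day 31 to day 120: paragraph 1 still requires two methods, while 5.1.2 and paragraph 3 require nothing. That is 120 − 30 = 90 days.

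**Pregnancy test.** Section 5.2 starts vorinostat on the same day as MK-3475, so both 72-hour windows end at the same visit.
- Negative urine test only: item 10 is met and 5.7.2 is not.
- Negative serum test: both are met.

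Section 7.1.5.1 does not settle this, because it lists a pregnancy test or serum hCG. The first-course flow chart row carries a footnote that is not in the available text, so it is not used here.

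**The case against.** The strongest reply is that the rules are cumulative. Section 5.1.2 points to 5.7.2, and 5.7.2 is itself an enrollment rule and a condition of participation. A site that applies the stricter text everywhere satisfies every section. This stands: a reader might infer that sites cannot comply with both sections, and the documents do not support that. What they lack is an instruction to take the stricter text when the criteria list states its own limit and its own test.

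Second, a reader might infer that the woman in the example is left with no contraception at all. Paragraph 3 of 5.7.2 rules that out on treatment and for 30 days. For the same reason it is not safe to say that women of 45 or over with more than 2 years of amenorrhea are exempt under every passage, since paragraph 3 as written exempts nobody.

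Third, the 'or' in 5.1.2, read literally, makes every non-sterilized woman of childbearing potential, and the definition gap at entry disappears. That is correct, but the 1-year clause would then do nothing for non-sterilized women, which is unlikely to be the intent. The urine and serum conflict is the same on either reading.

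Fourth, exclusion 12 bars a woman who "Is pregnant or breastfeeding, or expecting to conceive or father children within the projected duration of the trial", and Section 7.1.5.1 calls for a test by childbearing age, so the woman of 40 would probably be tested anyway. Both lower the risk. Neither sets an amenorrhea limit, a contraception duty or the type of test.

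**Conclusion.** The point holds as a patient-safety inconsistency of limited size. On the evident meaning of 5.1.2, it sets no contraception duty for non-sterilized, heterosexually active women under 45 with 1 to 2 years of amenorrhea, while 5.7.2 requires two methods or abstinence. The gap is two methods against adequate contraception on treatment and for 30 days after, then two methods against nothing for the following 90 days. The test conflict does not depend on that reading, and it covers any woman of childbearing potential entering the first course on a urine test alone. She is still tested within 72 hours.

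The documents do not say how many women are affected; probably few. The conclusion assumes the non-literal reading of 'or' for the definition, and a common last-dose date for the 90 days. No endpoint, sample size or analysis is touched, and nothing here suggests the trial's results would be affected.

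**What to change.** 1. In item 10 of Section 5.1.2, and for consistency in Section 7.1.5.1, require a negative serum pregnancy test within 72 hours before the first dose. Section 5.7.2 ties its rule to the first vorinostat dose, so it does not itself force the same change at second-course entry.
2. Put one definition of childbearing potential in Section 5.7.2, and have 5.1.2 and 5.1.4 refer to it in place of their own. Change 'or' to 'and'. Until the sponsor decides otherwise, use the strictest limit in paragraphs 1 and 2: a non-sterilized woman is of childbearing potential unless she is at least 45 and has gone more than 2 years without menses. Keep abstinence as an alternative to two methods.
3. State how the all-patient, 30-day rule in paragraph 3 fits with the two-method, 120-day rule, without relaxing either.

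The cost is amendment wording, plus a serum test and two-method contraception for a few more women. Under the interim limit these include women of 45 or over with 1 to 2 years of amenorrhea, whom paragraph 1 now treats as postmenopausal. Serum hCG is already in Table 9, and the 72-hour window does not change.

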3.2 Secondary Objective(s) & Hypothesis(es)

1. **Objective**: Determine the objective response rates and disease control rates of the combination of MK-3475 and vorinostat in patients with RMHNSCC and RMSGC

Hypothesis: The MK-3475 and vorinostat combination has clinical activity in RMHNSCC and RMSGC

2. **Objective:** Examine PD-L1 expression and T cell phenotype in archived tumor, on-treatment tumor biopsies, pre- and post-treatment blood samples and correlate these with clinical response to the drug combination.

Hypothesis: RMHNSCC and RMSGC express PD-L1. PD-L1 expression, tumor and serum T cell phenotype correlate with response to combination of MK-3475 and vorinostat.

3. **Objective:** Determine median overall survival and progression free survival in and RMHNSCC and RMSGC patients enrolled in the study

Hypothesis: Patients receiving MK-3475 and vorinostat will have statistically significant overall survival and progression free survival among patients with RMHNSCC and RMSGC.

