5.0 METHODOLOGY

5.1 Entry Criteria for Treatment at Trial Entry

5.1.1 Diagnosis/Condition for Entry into the Trial

Phase I run in: biopsy proven RMHNSCC with the following primary sites: nasopharynx, paranasal sinus, nasal cavity, skin/cutaneous sites. Patients with unknown head and neck primary sites will be enrolled. Patients with recurrent or metastatic squamous cell carcinomas of the head and neck (regardless of primary site) who are either unwilling to receive or have contraindications (deemed by treating physician) to standard systemic chemotherapy will also be eligible. Patients with biopsy proven RMSGC be eligible as well.

Since our center will be participating in a separate MK-3475 clinical trial (Keynote-40), the above group of patient will be prioritized for the phase I run in portion, and avoid overlap with Keynote -40.

Phase II expansion: biopsy proven RMHNSCC of any primary site (including unknown primary) and RMSGC will be eligible.

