5.1.2 Subject Inclusion Criteria

In order to be eligible for participation in this trial, the subject must:

- 1. Have disease progression by RECIST 1.1 criteria as determined by treating physician per investigator judgment within 3 months prior to enrollment.
- 2. Have received any number lines of prior systemic therapy (including systemic therapy in the curative intent setting).
- 3. Be willing and able to provide written informed consent for the trial and comply with the study visit requirements
- 4. Be \geq 18 years of age on day of signing informed consent.
- 5. Have measurable disease based on RECIST 1.1.
- 6. Have provided tissue from an archival tissue sample or newly obtained core or excisional biopsy of a tumor lesion.
- 7. Have a performance status of 0 or 1 on the ECOG Performance Scale.
- 8. Demonstrate adequate organ function as defined in
- 9. Table 1, all screening labs should be performed within 10 days of treatment initiation.

System	Laboratory Value
Hematological	
Absolute neutrophil count (ANC)	≥1,500 /mcL
Platelets	≥100,000 / mcL
Hemoglobin	$\geq 9 \text{ g/dL} \text{ or} \geq 5.6 \text{ mmol/L}$
Renal	
Serum creatinine OR Measured or calculated ^a creatinine	≤1.5 X upper limit of normal (ULN) OR
clearance	\geq 60 mL/min for subject with creatinine levels > 1.5 X
(GFR can also be used in place of creatinine or CrCl)	institutional ULN
Hepatic	
Serum total bilirubin	≤ 1.5 X ULN
AST (SGOT) and ALT (SGPT)	≤ 1.5 X ULN
Coagulation	
International Normalized Ratio (INR) or Prothrombin Time (PT)	≤1.5 X ULN unless subject is receiving anticoagulant therapy as long as PT or PTT is within therapeutic range of intended use of anticoagulants
Activated Partial Thromboplastin Time (aPTT)	≤1.5 X ULN unless subject is receiving anticoagulant therapy as long as PT or PTT is within therapeutic range of intended use of anticoagulants
^a Creatinine clearance should be calculated	per institutional standard.

Table 1 Adequate Organ Function Laboratory Values

- 10. Female subjects of childbearing potential should have a negative urine or serum pregnancy within 72 hours prior to receiving the first dose of study medication. If the urine test is positive or cannot be confirmed as negative, a serum pregnancy test will be required.

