5.1.3 Subject Exclusion Criteria

The subject must be excluded from participating in the trial if the subject:

- 1. Is currently participating in or has participated in a study of an investigational agent or using an investigational device within 4 weeks of the first dose of treatment.
- 2. Has a diagnosis of immunodeficiency or is receiving systemic steroid therapy or any other form of immunosuppressive therapy within 7 days prior to the first dose of trial treatment.
- 3. Has had a prior monoclonal antibody within 4 weeks prior to study Day 1 or who has not recovered (i.e., \leq Grade 1 or at baseline) from adverse events due to agents administered more than 4 weeks earlier.
- 4. Has had prior chemotherapy, targeted small molecule therapy, or radiation therapy within 2 weeks prior to study Day 1 or who has not recovered (i.e., ≤ Grade 1 or at baseline) from adverse events due to a previously administered agent.
 - Note: Subjects with \leq Grade 2 neuropathy are an exception to this criterion and may qualify for the study.
 - Note: If subject received major surgery, they must have recovered adequately from the toxicity and/or complications from the intervention prior to starting therapy.
- 5. Has a known additional malignancy that is progressing or requires active treatment. Exceptions include basal cell carcinoma of the skin, squamous cell carcinoma of the skin, or in situ cervical cancer that has undergone potentially curative therapy.
- 6. Has known active central nervous system (CNS) metastases and/or carcinomatous meningitis. Subjects with previously treated brain metastases may participate provided they are stable (without evidence of progression by imaging for at least four weeks prior to the first dose of trial treatment and any neurologic symptoms have returned to baseline), have no evidence of new or enlarging brain metastases, and are not using steroids for at least 7 days prior to trial treatment.

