8.0 STATISTICAL ANALYSIS PLAN

8.1 Statistical Analysis Plan Summary

The first 6 patients enrolled in this study will constitute the phase I component of the clinical trial. All patients enrolled in the study will be analyzed for the safety and efficacy endpoints of the study.

This will be a single arm phase II study which will enroll 35 patients in Cohort 1 and 35 patients in Cohort 2. All patients enrolled in the study (both in the phase I run in and phase II expansion) will be analyzed for the safety and efficacy endpoints of the study. For both Cohorts, using a 1-sided 0.07 level (exact) test with a null hypothesis of 20% response rate to the MK-3475 and vorinostat combination, an alternative of 40%, and 89% power (exact), 11/35 (31%) responses would be considered evidence to rule out an RR of < 20%. With 35 patients, frequencies can be estimated to within 17% with 95% confidence.

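### Inclusion criterion 13 is printed the wrong way round: it requires less than 5 years free of another primary cancer, and no other criterion restores a 5-year rule

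*Combined protocol and SAP*

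**What the plan says.** Section 5.1.2 (Subject Inclusion Criteria) opens with "In order to be eligible for participation in this trial, the subject must", so each numbered item under it is a condition of entry. Item 13 reads "Patient is < 5 years free of another primary malignancy, except". Two exceptions follow: (a) basal cell carcinoma or in situ cervical carcinoma, and (b) a primary judged clinically unimportant that needs no active intervention.

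Two exclusions in section 5.1.3 bear on the same patients:

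- Exclusion 5 is the only other criterion specifically about second cancers: "Has a known additional malignancy that is progressing or requires active treatment". It continues: "Exceptions include basal cell carcinoma of the skin, squamous cell carcinoma of the skin", and also excepts in situ cervical cancer after potentially curative therapy.
- Exclusion 10 is a general clause: "Has a history or current evidence of any condition, therapy, or laboratory abnormality that might confound the results of the trial". It applies in the treating investigator's opinion.

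On the analysis side, section 3.2 makes it a secondary objective to "Determine median overall survival and progression free survival", and section 8.1 states: "All patients enrolled in the study will be analyzed for the safety and efficacy endpoints of the study".

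**The concern.** A 5-year criterion on other primary cancers normally keeps out patients whose recent second cancer could relapse or kill during follow-up. Item 13 does the opposite, because wording suited to an exclusion sits under an inclusion stem.

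Three things are at stake:

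- **Deviations.** Section 7.1.1.2 requires every criterion to be reviewed for each subject. A site that follows the evident intent breaks the printed rule, and a site that follows the printed rule admits the wrong patients.
- **Uneven screening.** Patients with a past second cancer may be handled differently from one screener to the next.
- **Interpretation of secondary endpoints.** A patient with a recent but inactive second cancer could enter. A death from that cancer would be an overall survival event. Whether its relapse would count as progression is not stated: section 8.2 says only that time runs from study entry to the corresponding event.

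**Working it through.** The main check is of logic and text.

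**Step 1. Apply item 13 as printed.** The test is years free of another primary < 5, with no exception applying. The last column is the rule that the exceptions imply, namely that recent second cancers are kept out.

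| Patient | Item 13 as printed | Exclusion 5 | Implied rule |
|---|---|---|---|
| Significant second cancer, inactive, 2 years free | 2 < 5: meets | Not barred | Kept out |
| Second cancer, inactive, 7 years free | 7 is not < 5: fails | Not barred | Admitted |
| Never had another cancer | No date to count from: cannot be shown to meet | Not barred | Admitted |

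If the third patient's cancer-free time is counted from birth, it is at least 18 years (inclusion 4), and the patient fails outright.

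**Step 2. Test the exceptions against each reading.** Under the printed reading, a basal cell carcinoma 2 years ago already satisfies the item, so an exception for it gives no relief. Under a rule against recent second cancers, the same exception lets that patient in, which is what such an exception is for. The exceptions therefore fit an exclusion worded as less than 5 years free, or an inclusion with the opposite sign. They do not fit the inclusion as printed.

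**Step 3. Look for another 5-year rule.** Sections 5.1.1 to 5.1.4 were read for any malignancy-free interval.

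- Exclusion 5 looks at current activity and has no time window.
- Exclusion 10 has no time window and rests on judgement.
- The second-course criteria in 5.1.4 contain no rule on second cancers.

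No 5-year interval appears outside item 13.

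**Step 4. Compare the two exception lists.** Exclusion 5 names squamous cell carcinoma of the skin as an exception; item 13 does not. A past skin squamous cancer separate from the study tumour is thus excepted by name under one rule, and under the other only if it is judged to fit exception (b). Section 5.1.1 accepts study tumours at "nasopharynx, paranasal sinus, nasal cavity, skin/cutaneous sites", but that concerns the index cancer and adds little.

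**Step 5. Size per patient.** The plan's precision figure in section 8.1 is 17 percentage points at n = 35. It reproduces: 1.96 × √(0.5 × 0.5 / 35) = 0.166, or 17 points. One patient is 1/35 = 0.0286, or 2.9 points, and 0.0286 / 0.166 = 0.17 of that margin. This scale applies to a simple proportion. It does not convert into a shift in a Kaplan-Meier median.

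**The case against.** The strongest reply is that nobody could apply the item literally. It would turn away, or leave unassessable, every patient without another cancer, so sites will read it as intended. Exclusion 5 still removes active second cancers, and exclusion 10 lets the investigator refuse a confounding history. Exception (b) would admit clinically unimportant cancers even under a corrected rule. The patients wrongly admitted are then only those with a recent, significant but inactive second cancer, screened literally and not caught by exclusion 10.

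This stands as a limit on the practical effect, but it does not make the printed rule right. The enrolment record is judged against the text, and section 5.8 allows withdrawal of a subject whose enrolment was inappropriate.

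Four narrower points also have force:

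- The 1/35 figure shows the weight of one patient and is not evidence of harm to median survival.
- Counting a relapse of the other cancer as progression is only a possibility.
- The two exception lists serve different tests (time since a past cancer, and current activity), so they need not be identical.
- The text was read from a PDF and the point turns on one character. A misread sign cannot be fully excluded, but other inequality signs in the same list read sensibly, so it is unlikely.

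**Conclusion.** The concern holds. Item 13 is reversed under its governing stem, and no other criterion supplies a 5-year interval. It is an operative eligibility rule and should be corrected.

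The consequence is modest: mainly deviations and inconsistent screening, with possible entry of some patients whose recent, inactive second cancer could later affect the secondary survival endpoints. The documents give no prevalence of second cancers, so the number affected cannot be estimated and none is claimed. The response-rate design in section 8.1 does not change.

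The conclusion rests on two assumptions: that the intended direction is the one implied by the item's own exceptions and by exclusion 5, and that the sign is printed in the source as it reads here.

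**What to change.** Confirm the sign in the source document, then correct item 13 in one of two ways:

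1. Move it to section 5.1.3, worded to follow the exclusion stem, so that a subject less than 5 years free of another primary malignancy is excluded, with the exceptions kept.
2. Keep it in section 5.1.2, reverse the inequality so that it requires at least 5 years free, and state that patients with no other malignancy also qualify.

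Then reconcile it with exclusion 5: say how the time window and the current-activity test work together, and whether squamous cell carcinoma of the skin is excepted under both. The final second-malignancy rule is the sponsor's decision.

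The cost is a short amendment to item 13 and, where needed, exclusion 5, with IRB approval before implementation as section 10.5 requires. Sample size, alpha, power and the analysis stay as they are.
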